1.0 Objectives

Table 1: Objectives, Endpoints, and Justifications					
Objectives	Endpoints	Justification			
Primary	Primary	Primary			
Evaluate the effectiveness of	ED-15 score	ED-15 is an evidenced-based			
oral naltrexone tablets in		metric of eating disorder			
pediatric and adolescent eating		symptom severity and			
disorders, particularly anorexia		frequency.			
nervosa and bulimia nervosa, as					
compared to placebo.					
Secondary	Secondary	Secondary			
Evaluate the effect of oral	Improvement on Eating	Naltrexone has some effect on			
naltrexone on desire to self-	Disorder Examination	desire to self-harm, and this can			
harm and impulsivity in patients	Questionnaire (EDE-Q), Patient	be examined in eating disorder			
with eating disorders	Health Questionnaire-9 (PHQ-	patients. EDE-Q, GAD-7, PHQ-			
	9), Generalized Anxiety	and BIS/BAS measure other			
	Disorder-7 (GAD-7), Alexian	features of eating disorder			
	Brothers Urge to Self-Injury				
	Scale (ABUSI), and Behavioral				
	Inhibition System/Behavioral				
	Activation System score				
	(BIS/BAS), need for escalation of				
	level of care, desire to restart				
	study article, and rate of weight				
	restoration.				
Tertiary/Exploratory	Tertiary/Exploratory	Tertiary/Exploratory			
none					

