3.2 Exclusion Criteria

Create a numbered list of the exclusion criteria that define who will be excluded in your study.

- Diagnosis of intellectual disability
- History of known genetic or neurologic disease
- Need for treatment with opioid painkillers
- Weight <25kg
- Inability to swallow pills
- Lack of proficiency in written or spoken English
- Urine drug screen positive for opioids at enrollment
- Positive serum pregnancy test at enrollment
- Lactation
- Elevation of three times the upper limit of normal for age in either alanine aminotransferase (ALT) or asparagine aminotransferase (AST).
- High risk of suicide at enrollment on Columbia Suicide Severity Rating Scale (C-SSRS, for participants age 18)²⁰ or Ask Suicide Screening Questions (ASQ, participants age 13 to 17)²¹
- Current Naltrexone use

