3.3 Early Withdrawal of Subjects

3.3.1 Criteria for removal from study

Insert subject withdrawal criteria (e.g., safety reasons, failure of subject to adhere to protocol requirements, subject consent withdrawal, disease progression, etc.).

- New need for medical hospitalization for malnutrition or eating disorder
- Need for escalation of level of care for eating disorder, that is, requirement for inpatient or residential-level eating disorder care
- New need for opioid painkillers
- Subject consent withdrawal
- Inability to adhere to protocol requirements
- New diagnosis of pregnancy
- New elevation of three times the upper limit of normal for age in either alanine aminotransferase (ALT) or asparagine aminotransferase (AST).

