When patients come into the clinic for either an initial medical screening appointment for their enrollment in PHP or in the initial psychiatry appointment that they have when they enroll, a staff member will assess the patient's eligibility in participating in the research study using the information in the patient's chart and information that is obtained in the appointment. The primary screening criterion will be that the potential subject choses to enroll. Potential subjects who are not medically appropriate for PHP or who do not desire to attend PHP will not be screened any further for the purposes of this study. The only screening that must take place is a point-of-care pregnancy test for postmenarchal (having had at least one menstrual cycle) females with amenorrhea (absent or missed menses)—which is standard of care for these patients regardless of their decision to enroll or not—and a urine drug screen, as oral naltrexone may cause immediate opioid withdrawal if administered to a person with opioid-positive urine. Potential subjects with a positive urine pregnancy test or urine drug screen positive for opioids will not be enrolled. Urine drug screen and urine pregnancy test are specifically outlined in the study consent document.

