7.1 Study Design

Describe and explain the study design.

This is a double-blind, randomized, placebo-controlled study. We have developed the following schedule of events. All events with a superscript $^{\circ}$ are for study purposes only and are not part of the standard of care:

	Pre-Enrollment Screening: Medical	Enrollment	Week 1	Week 2	Week 3	Week 4	Week 5	Week 6 (end of treatment	Week 8-9 (post- treatment)	Six Months
Intervention								_	>	
Initial Medical Assessment	Х									
Subsequent Medical Assessment, including comprehensive review of systems			x		x		x		х	х
Initial Psychiatry Assessment	X									
Subsequent Psychiatric Assessment, including suicidal ideation			х	х	х	х	х	х	х	х
Discussion of risks and benefits, inclusion and exclusion criteria ^o		х								
Consent/Assent ^o		Х								
\$25 Greenphire Clincardo		Х								х
Urine Drug Screen ^o		Х								
Serum Pregnancy Test (female participants)°		х								
Urine Pregnancy Test (female participants)°					х			х		
Administer Study Article ^o			Х	Х	х	Х	Х	х		
EKG	X									
AST	X				Xº			Xº		
ALT	Х				χ°			Xo		
Total Bilirubin	Х				Xº			Xº		
Direct bilirubin	Х				Xº			Xº		
Heart Rate	Х		Х	Х	Х	Х	Х	Х	Х	Х
BMI	X		Х	Х	Х	Х	Х	X	Х	Х
Height	X		Х	X	X	X	Х	X	X	Х
Weight	X		X	X	X	X	X	X	X	X
Blood Pressure	X		X	X	X	X	X	X	X	X
Temperature Adverse event monitoring ^o	Х		X	x	x	x	x	x	X	X
Suicidal Ideation Screening (ASQ			^	^	^	^	^			
for age <17or C-SSRS for age 18+)		х	Х	Х	х	Х	Х	х	Х	Х
ED-15		Х	х		х			Х	X	х
EDE-Q		Х	х		х			Х	X	Х
ABUSI°		Х	Х		х			Х	Х	Х
GAD-7		Х	х		х			Х	Х	Х
PHQ-9		Х	Х		Х			Х	X	Х
BIS/BAS°		Х	Х		Х			Х	Х	Х

Note: Medical assessments may occur in weeks 1,3 etc or 2,4 etc depending on standard of care for that patient. As long as patients are seen within a 14 day interval (2 week timeframe), the exact week intervals (1,3 or 2,4) may vary. Additionally, the 6 month follow up appointment may take place any time between 5-7 months after study enrollment ends.

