The subject will be provided with oral naltrexone or placebo weekly from the MSHMC research pharmacy. Subjects will be given one weeks' worth of medication at a time. Subjects will be randomized at enrollment to receive either study drug (naltrexone) or placebo. Participants or parents of minor participants will be provided study drug or placebo following completion of urine drug screen and consent/assent. Patients will take the medication daily while they are in programming; after completion of programming or withdrawal from the study they will no longer be given study medication. For subjects who are enrolled in child PHP and who eat meals with parents, the families may choose to administer study drug during meals at programming. For adult patients enrolled in adult programming, subjects may choose to self-administer the medication.

On their first contact with PHP, all patients in Adult PHP complete various eating disorder indices as a part of routine care, including the ED-15, PHQ-9, GAD-7, and EDE-Q. This battery of indices is repeated every 3 weeks while a patient is in programming.

For those who are enrolled in this study, they will complete their routine indices, in addition they will also complete the BIS/BAS and the ABUSI at enrollment and at weeks 1, 3, and 6 while enrolled in the study. Participants will also be asked to take the routine indices (ED-15, EDE-Q, PHQ, GAD, BIS/BAS, and ABUSI) at week 8 or 9 for a post-treatment evaluation. These will be taken in an in-person medical appointment or electronically via RedCap

6 months after enrollment, subjects will be sent copies of ED-15, EDE-Q, PHQ, GAD, BIS/BAS, and ABUSI indices either in an in-person medical appointment or via RedCap to complete. If the patient returns for medical follow-up between 5 and 7 months after enrollment, their height, weight, and body mass index will also be recorded to determine if weight restoration was maintained.

Patients in Child PHP typically complete a different inventory every three weeks as part of routine care. If a patient choses to participate in this study they will be asked to complete the same surveys as participants in Adult PHP (ED-15, GAD-7, and PHQ-9), and they will receive the same amount and type of compensation as those who already take them as part of standard of care.

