7.1.2 Visit 2 or Day 2 or Post-test, etc. (If applicable)

Provide a description of what procedures will be performed on visit 2 or day 2 or post-test in order of how these will be done. If your study involves more than two sessions or visits replicate this section for each additional session or visit (e.g., 7.2.3, 7.2.4, etc.).

On the first day of study participation after enrollment, all subjects will receive a complete set of vital signs (including heart rate, blood pressure, respiratory rate, temperature, and weight) and urine drug screen including screening for opioid substances prior to receipt of their first dose of study article.

Routine care during PHP for any participant includes every-other-week in-person medical exams for the duration of the patient's stay in program, as well as frequent appointments following completion of PHP, until discharge from clinic. At each medical appointment, patients receive a comprehensive physical exam including complete vital signs as above, and are routinely asked about mood changes, physical changes, difficulty or ease of adhering to routine program protocols, etc. All patients participating in PHP complete routine surveys to assess eating disorder recovery at intake and every three weeks until completion of program. For participants in this study, the documentation of their three- and six-week appointments will be reviewed for evidence of adverse effects related to study participation by study personnel. Participants will also complete two additional surveys, the ABUSI and BIS/BAS, beyond their routine PHP surveys at weeks three, six, and eight/nine. Routine medical testing will be obtained according to clinical need at all medical visits, regardless of participation in this study, for all patients participating in PHP.

For patients participating in this study, liver function panel will be obtained once every 3 weeks at no cost to study participants for the purpose of monitoring drug safety, as well as completion of all of the relevant study indices

The vast majority of patients who require PHP have a routine medical follow-up at approximately six months; for those who do not this appointment will be made at no cost to the participant. At this appointment, participants will again undergo a comprehensive physical

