7.3.2 Treatment Regimen

Describe dose, route of administration and treatment duration. Include information about dose adjustments.

All subjects receiving study medication will receive oral naltrexone 50mg oral tablets, blinded as described above. All subjects receiving placebo will receive methylcellulose, blinded as described above. All capsules, regardless of contents, will be administered by mouth once daily, at a time of day to be chosen by the study participant.

In pediatric autism literature, doses between 0.5-2 mg/kg are described^{8,11,22,22-25}, though in adult eating disorder literature doses of 50-100mg are described^{13,14,16-18}. Food and Drug Administration labelling of oral naltrexone for treatment of alcohol use disorder and opioid receptor blockade describe an appropriate maintenance dose of 50mg per day⁷. Therefore subjects will receive 50mg of oral naltrexone a day if they are randomized to the medication group. Patients with body weight less than 25kg are excluded from the study so that no participant will exceed the maximum described pediatric dose of 2 mg/kg. Participants receiving

study article will receive 25mg of naltrexone for three days, followed by increase to study dose of 50mg/day The maximum daily dose is 50mg.

Participants will take study medication daily while they are in PHP or for six weeks total. That is, if a participant is in PHP for three weeks, they will take the study medication for the entirety of their time in PHP and then continue to take the medication for three additional weeks after discharge from PHP. If a participant is in PHP for twelve weeks—which is quite uncommon—they will only take study medication for six weeks.

For participants who complete PHP early, they will be asked to complete the same battery of surveys at 3 and 6 weeks, at weeks 8/9 for post-treatment evaluation, and at 6 months. Survey responses will be obtained via RedCAP for participants not on-site at time of survey completion.

Participants who, upon completion of the study, feel that they had significant benefit from the study article which lost upon withdrawal of the study article, are eligible for open label oral naltrexone therapy if desired. Participants will be asked at subsequent medical and behavioral health follow-up appointments if they felt they benefitted from the study article. If they feel they did, they will be offered a prescription for oral naltrexone to start at 25mg/day for three days and then 50mg a day after.

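### The open-label naltrexone offer in section 7.3.2 omits the opioid-negative urine screen that the protocol requires before a first dose of study article

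*Combined protocol and SAP*

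**What the plan says.** The last paragraph of section 7.3.2 sets three conditions for open-label naltrexone: the participant feels there was significant benefit, the benefit was lost when study article stopped, and the participant wants the drug. Benefit is asked about at later medical and behavioral health appointments. Then: "If they feel they did, they will be offered a prescription for oral naltrexone to start at 25mg/day for three days", rising to 50 mg a day. The paragraph names no laboratory test and no treatment arm. Its only statement on timing is that the offer follows completion of the study.

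For blinded study article the rules are stricter. Section 3.2 excludes on "Urine drug screen positive for opioids at enrollment". Section 4.2.4 gives the reason: "oral naltrexone may cause immediate opioid withdrawal if administered to a person with opioid-positive urine". Section 7.2 (Study Procedures) releases study drug or placebo only after the urine drug screen. Section 7.1.2 asks on the first day of participation for a "urine drug screen including screening for opioid substances prior to receipt of their first dose of study article". Section 7.3.6.5 excludes anyone with an opioid prescription, and section 3.3.1 removes a participant for "New need for opioid painkillers".

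In the section 7.1 schedule, the "Urine Drug Screen" row is marked once, at enrollment, with the symbol that means for study purposes only and not standard of care. Section 7.1.1 says the result is not entered in the medical record.

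**The concern.** The protocol regards an opioid screen as necessary before a person takes naltrexone under the trial, and it names the harm the screen prevents. The open-label offer is another point at which a person may begin naltrexone under the same document. It repeats the starting titration used for the blinded course (25 mg for three days, then 50 mg) but not the check that precedes it. Because the offer rests on the participant's own impression of benefit, someone who received placebo can qualify. For that person the open-label prescription would be the first naltrexone exposure under the protocol.

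What is at stake is precipitated opioid withdrawal in a participant whose opioid use is undisclosed, or began after study article stopped. The trial enrolls from age 13. The missing screen has no bearing on how efficacy outcomes are measured or compared.

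**Working it through.** The plan states no figure to reproduce. The check sets the two starts side by side, asks whether anything else fills the gap, and then works out how old the last screen could be.

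**Step 1. Requirements at each start**

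| Requirement | Blinded first dose | Open-label start (7.3.2) |
|---|---|---|
| Opioid-negative urine screen | Yes (3.2, 4.2.4, 7.2, 7.1.2) | Not stated |
| No opioid prescription | Yes (7.3.6.5) | Not stated |
| 25 mg for three days, then 50 mg | Yes (7.3.2) | Yes |
| Depends on arm | Randomized | No condition on arm |

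**Step 2. Does usual care supply the screen?**

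- The schedule marks the urine drug screen as outside standard of care.
- Section 7.1.1 keeps the result out of the chart. This matters only partly, since anyone enrolled should have screened negative. The more important point is that no later screen is scheduled at all.
- Section 7.3.6.5 tracks medication by reconciliation at the every-two-week visits while the patient is in the partial hospitalization program. It describes no equivalent afterward.
- Section 7.1.2 allows testing by clinical need at any medical visit. A prescriber may therefore screen, but nothing requires it.

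**Step 3. Age of the last scheduled screen at an open-label start**

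Inputs: the six-week course (7.3.2); the post-treatment visit at week 8 or 9 (7.1 schedule); the six-month visit, which section 7.2 (Study Procedures) places as "If the patient returns for medical follow-up between 5 and 7 months after enrollment"; and 365.25 / 12 = 30.44 days per month. Weeks are counted from the enrollment or first-day screen.

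- Earliest offer after a completed course: 6 × 7 = 42 days.
- Offer at week 8 or 9: 8 × 7 = 56 days to 9 × 7 = 63 days.
- Offer at the six-month visit, by section 7.2: 5 × 30.44 = 152 days to 7 × 30.44 = 213 days.
- The note under the section 7.1 schedule instead counts the 5 to 7 months from the end of study enrollment. If that means the end of week 6 (an assumption), the range is 42 + 152 = 194 days to 42 + 213 = 255 days.

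For comparison, section 7.1.2 puts a screen on the same day as the blinded first dose.

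**Step 4. How many participants?**

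Section 8.1 plans 30 per arm, so 0 to 30 placebo participants could start this way. That range is only the arm size. The documents give no rate at which participants would report a lost benefit and accept the offer.

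**The case against.** The strongest reply is that the screening rule applies to study article supplied by the research pharmacy, whereas the offer is an ordinary prescription written at a follow-up visit. On that view, checks before prescribing belong to the clinician. Section 7.3.2 also places the offer after completion of the study, and section 7.2 (Duration of Participation) runs participation to the six-month visit, so the offer may fall outside the trial altogether. Known opioid need is already covered by sections 3.3.1 and 7.3.6.5. What remains is undisclosed or new opioid use in someone who also reports a lost benefit and wants the drug.

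Much of this stands. It makes the point minor, and it makes any single figure for the age of the screen conditional on an offer date the plan does not fix. It does not remove the point. The offer, its conditions and its dose are written into the Treatment Regimen section, and by the protocol's own marking usual care does not include the screen. A later offer date also makes the last screen older.

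Three stronger readings are tempting, and the documents do not support them:

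- *The absence of an unblinding step is itself a defect.* Section 18.6 gives a general route to unblind through the pharmacy, with opioid need as an example, not a limit. No harm follows from staying blinded other than the missing screen, and screening both arms deals with that.
- *Liver and pregnancy tests have lapsed in the same way.* At week 8 or 9 the week-6 results are only 56 − 42 = 14 to 63 − 42 = 21 days old. Section 9.8 already follows raised AST/ALT until normal, and section 10.0 describes urine pregnancy tests every three weeks throughout the study.
- *Section 9.2 ends all laboratory evaluation once the patient leaves the program.* The word weekly in that sentence may govern the whole list, so it cannot bear that weight.

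**Conclusion.** The point holds as a minor participant-safety omission. Followed as written, section 7.3.2 allows naltrexone to be started, possibly for the first time under the protocol, without the opioid-negative screen the protocol requires before study article. The last scheduled screen would be about 8 to 9 weeks old at the post-treatment visit, and about 5 to 7 months old or more if the offer follows the six-month visit.

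This rests on two readings. The first is that the offer is open to both arms, which is inferred from the absence of any arm condition. The second is that the prescriber is free to screen but not obliged to. The number of participants affected cannot be estimated from the documents. The missing screen does not affect the efficacy results.

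**What to change.** At the end of the last paragraph of section 7.3.2, add:

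*Before an open-label prescription is issued, the participant must have an opioid-negative urine drug screen and no current opioid prescription.*

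The sentence applies to both arms, so nobody need be unblinded, and it works whenever the offer is made. No new schedule column is needed. A mandatory AST/ALT or pregnancy check should not be attached. In particular, a limit of three times the upper limit of normal, borrowed from section 3.2, would be looser than section 9.8, which stops study article at any value above normal.

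The cost is one urine screen, of a kind the protocol already uses, for each participant who accepts: at most 60 if every planned participant did (30 × 2).

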7.3.3 Method for Assigning Subject to Treatment Groups

Describe the randomization process and how the associated treatment assignment will be made.

Subjects will be randomized at enrollment using RedCap. Randomization will be stratified by age (16 and under or 17 and older) and diagnosis (anorexia nervosa binge/purge subtype and bulimia nervosa or OSFED with bingeing or purging behaviors), equaling 4 strata.

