5.2 Obtaining Informed Consent

5.2.1 Timing and Location of Consent

Describe where and when the consent process will take place.

Consent and assent will take place at recruitment. Potential subjects will be recruited and enrolled at the completion of either their medical intake appointment for PHP or following the completion of their first psychiatry appointment on their first day of PHP. This will take place in a private therapy or medical room in the Adolescent Medicine and Eating Disorders Clinic, on the 2nd floor of the Briarcrest building.

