REDCap, will be used to store the surveys. Participants will be sent the link to the battery of surveys via email at the designated times listed above. The link will redirect them to the programmed surveys in REDCap. Their responses will be stored in REDCap until data is exported and stored on the secure file server (hersheymed.net/files). Only authorized study personnel will have access to the REDCap surveys and folder access on the secure network.

At initial contact with the eating disorders clinic, all patients receive an initial battery of laboratory tests as a part of the standard of care for eating disorder. These tests include liver function assays and transaminase levels. Further information about liver function test and monitoring for drug-induced liver injury is outlined in section 9.0.

7.1.1 Enrollment.

Provide a description of what procedures will be performed on visit 1 or day 1 or pre-test in order of how these will be done. If your study only involves one session or visit, use this section only and indicate 7.2.2 as not applicable.

As discussed above, patients can be enrolled at either their initial medical or initial psychiatric appointments for participation in the appropriate PHP for eating disorder.Per Joint Commission regulations of partial hospitalization programs for any psychiatric diagnosis, a complete blood count, blood chemistry, liver function test, urinalysis, and electrocardiogram must be obtained at enrollment and other studies at the program's discretion. If all necessary bloodwork, EKG, and urine studies have been obtained within the last two weeks, these results will be tracked down, recorded into the medical record, and any necessary and routine studies that have not been completed prior to this appointment will be completed at enrollment.

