For patients enrolling at their medical appointment: after completion of the medical appointment, the study coordinator will approach the patient and family (if the patient is under 18 years of age), and discuss the study. The study coordinator will review the consent/assent forms, and after completion of the appointment the patient will be asked to obtain their routine studies (unless they have already been obtained as described above) within the coming seven days. A urine drug screen will be obtained at no cost to the participant and its results will not be placed into the medical record. Patients screening positive for any opioid will be excluded from the study and offered referral for addiction counseling. For potential female subjects, a serum pregnancy test will also be obtained at this time. Patients screening positive for pregnancy will be referred for options counseling

For patients enrolling at their psychiatric appointment: Joint Commission regulations regarding obtaining lab studies are unchanged, regardless of initial appointment location. All patients in PHP have biweekly medical appointments as a part of routine care, and routine enrollment labs are typically

obtained at the first medical appointment after first psychiatric appointment during the first seven days of programming. Labs will be ordered at that appointment and obtained within seven days, or entered into the medical record if obtained elsewhere, at that time. A urine drug screen will be obtained at no cost to the participant and its results will not be placed into the medical record. Patients screening positive for any opioid will be excluded from the study and offered referral for addiction counseling. For potential subjects who are female, a serum pregnancy test will also be obtained at this time. Patients with a positive pregnancy test will be referred for options counseling.

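### The protocol contradicts itself on whether AST/ALT must be known before randomization and first dose, so someone excluded by section 3.2 could be randomized and dosed first

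*Combined protocol and SAP*

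**What the plan says.** The exclusion in section 3.2 reads "Elevation of three times the upper limit of normal for age in either alanine aminotransferase (ALT) or asparagine aminotransferase (AST" and takes effect at three times ULN.

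Three places require that result before enrollment. Section 5.2.2 has the medical provider check every criterion first, section 6.2.3 makes normal bloodwork a precondition of participation, and the section 7.1 schedule marks AST and ALT in the pre-enrollment column (next at weeks 3 and 6).

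The operational sections read differently:

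- **Screening (4.2.4):** "The only screening that must take place is a point-of-care pregnancy test for postmenarchal" females with amenorrhea, together with a urine drug screen. AST/ALT is not listed.
- **Consent and enrollment (5.2.1):** at the end of the medical intake visit or "following the completion of their first psychiatry appointment on their first day of PHP".
- **Randomization (7.3.3):** "Subjects will be randomized at enrollment using RedCap". Section 7.2 Study Procedures says the same.
- **Lab timing, general (7.1.1):** "any necessary and routine studies that have not been completed prior to this appointment will be completed at enrollment".
- **Lab timing, medical route (7.1.1):** after the study discussion, "the patient will be asked to obtain their routine studies (unless they have already been obtained as described above) within the coming seven days".
- **Lab timing, psychiatry route (7.1.1):** routine labs are typically "obtained at the first medical appointment after first psychiatric appointment during the first seven days of programming". The next sentence adds: "Labs will be ordered at that appointment and obtained within seven days".
- **Release of study article (7.2, 7.1.2):** consent or assent, urine drug screen and vital signs are named. AST/ALT and the serum pregnancy result are not.

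**The concern.** No sentence makes randomization or dispensing wait for a resulted AST/ALT. Staff who follow 4.2.4, 7.1.1, 7.2 and 7.1.2 literally could randomize and dose a person whom 3.2 excludes. Elevated transaminases are the first risk listed for this drug in section 10.0, and the trial enrolls minors.

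Three consequences follow:

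- An ineligible participant is found only after randomization and leaves treatment from within the randomized set. Section 3.3.1 provides withdrawal only for a new elevation, and section 8.3 does not say how participants found ineligible after randomization are analysed.
- If blood is first drawn after dosing has begun, there is no clean pre-dose liver baseline for that person.
- Without that baseline, an elevation that predates the drug could be read as an on-study one. Section 9.8 suspends the study for two participants above 3x ULN or one above 5x ULN.

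**Working it through.** The plan states no figure on this point, so there is nothing to reproduce. The check sets the timing statements side by side and then sizes the gap.

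**Step 1. Is there a gate?** Sections 5.2.2, 6.2.3 and the 7.1 schedule place the result before enrollment. Section 7.1.1 places the blood draw at enrollment in one sentence and up to seven days after the enrolling visit in the next paragraphs. Because randomization is at enrollment, these cannot all be followed for someone without recent labs. Even a sample taken at enrollment is not a result in hand at enrollment. Two further details point the same way. Section 7.1.1 states what follows a positive opioid screen or pregnancy test but nothing for a liver result. Section 9.4 lists the safety data collected at enrollment as vital signs, serum pregnancy tests and urine drug screens, without AST/ALT.

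**Step 2. How long is the gap?**
- Medical route: up to 7 days after the visit.
- Psychiatry route: up to 7 days, if labs are drawn in the first week of programming.
- Psychiatry route, looser reading: if the appointment at which labs are ordered is a medical visit as late as day 7, and a further seven days are allowed, 7 + 7 = 14 days.

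**Step 3. Exposure in the gap.** Inputs are seven capsules per weekly bottle (7.3.6.1) and 25 mg for three days, then 50 mg daily (7.3.2). Assume dosing starts the day after enrollment. The documents give no time from draw to result, and none is counted.
- 7 days: 3 × 25 + 4 × 50 = 275 mg (active arm).
- 14 days: 3 × 25 + 11 × 50 = 625 mg (active arm).
- With labs already on file, exposure is zero. It may also be zero on the medical route if the partial hospitalization program (PHP) starts later than the labs.

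**Step 4. Effect on the suspension rule.** Two participants out of the planned 60 is 2/60 = 3.3%. The documents give neither the number with late labs (n) nor the share already above 3x ULN (p), so both are assumptions. The chance that at least two such people are present is P(X ≥ 2) = 1 − (1−p)^n − n·p·(1−p)^(n−1):

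| n with late labs | p = 1% | p = 2% |
|---|---|---|
| 15 | 0.010 | 0.035 |
| 30 | 0.036 | 0.121 |

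Over these assumed ranges the chance is about 1% to 12%.

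**The case against.** The strongest reply is that a gate exists once the sections are combined. Section 5.2.2 verifies all criteria before enrollment, 6.2.3 requires bloodwork before enrollment, and randomization happens at enrollment, so randomization follows verified labs. On this view enrollment is a window rather than a moment. Section 7.1.1 still calls people potential subjects when the pregnancy test is drawn, and 4.2.4 has staff use chart information to judge eligibility, so its short list may mean only testing beyond chart review.

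That reading is possible, and 5.2.2, if enforced, would prevent the problem. It is not secure. Section 5.2.1 enrolls people at the end of the appointment, 5.2.2 is advisory wording in a section on undue influence, and the steps that staff will actually follow name other conditions and omit this one.

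Other parts of the reply do stand:

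- Section 7.2 says every patient has liver tests at first contact with the clinic, and 4.2.3 places the psychiatry appointment after the medical one, so the affected group may be small.
- The dose never exceeds 50 mg a day, liver results are reviewed weekly (9.1), and 9.8 stops study article for any value above normal, so exposure should be short.
- Suspension comes with a safety evaluation, in which a pre-existing elevation could be recognized if there is evidence of it.
- The pregnancy point is weaker, because 3.2 and the schedule both place the serum test at enrollment. What remains is that its result is not named as a condition for dispensing.

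**Conclusion.** The concern holds. The current text gives conflicting rules on when AST/ALT must be known, and following the operational steps as written permits dosing of a participant excluded by 3.2. It is a risk that the text allows, not one that it prescribes, and it is confined to participants without recent labs.

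The firm reading gives a gap of up to 7 days and up to 275 mg in the active arm, assuming dosing starts the day after enrollment. The 625 mg figure also depends on how one ambiguous sentence in 7.1.1 is read. The 1% to 12% chance of two pre-existing elevations only illustrates assumed rates. The effect on power is small and no case is made on it. The point should be fixed because it concerns eligibility and liver safety and the remedy is cheap.

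**What to change.** State in 7.2 Study Procedures, 7.1.2 and 7.3.3 that REDCap randomization and first dispensing both require resulted AST/ALT, serum pregnancy test (female participants) and urine drug screen, all meeting section 3.2. The rule should cite 3.2 because 6.2.3 speaks of normal bloodwork while 3.2 excludes only at three times ULN. Bring 4.2.4 and the lab-timing sentences of 7.1.1 into line with this rule and with 5.2.2, 6.2.3 and the 7.1 schedule. Count anyone who fails before that point as a screen failure, outside the randomized set.

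The cost is protocol wording and an eligibility check in REDCap, with no new tests. The downside is that participants without recent labs start study article some days later.
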